8. CORRELATIVE/SPECIAL STUDIES – N/A

9. STUDY CALENDAR

- All research activity requiring patient participation occurs during the image-guided liver thermal ablation procedure on day 1. The only research activities are the one or two perfusion PET scans on day 1. All other calendar events fall within our routine clinical practice.

CONFIDENTIAL

This document is confidential. Do not disclose or use except as authorized.

- **Arm 2:** the calendar for Arm 2 is identical to Arm 1; FDG PET/CT is substituted for Ammonia PET/CT
- Follow-up imaging examinations are performed as part of routine clinical practice and do not require extra patient time or commitment.

	Visit 1	Visit 2	Visit 3	Visit 4
	Screening	Day 1	Day 2-30	Day 90-365
Medical History & Physical Exam	X			
Blood Test	X			
Pregnancy Test	X			
Liver tumor ablation		X		
Perfusion PET/CT		X		
MRI, CT or PET/CT scan			X	X

10. MEASUREMENT OF EFFECT

Drug response is not an endpoint of this trial. No therapeutic drugs are investigated in this trial. Patients undergoing liver ablation procedures will undergo follow-up contrast-enhanced MRI or CT at 24 hours (but not more than 30 days) after the ablation and then at 3-months to one year after the ablation. While obtaining a contrast-enhanced MRI or CT is routinely performed by our team at 24 hours, there are occasionally patient-specific clinical factors that may make it preferable to obtain the initial post-procedure scan up to 30 days later. This does not compromise our assessment of study endpoints. Then at least one scan is obtained between 3-months and one year, depending on routine clinical requirements. If there is severe renal insufficiency with $EGFR < 30$, the patient cannot be enrolled. CT and MRI with contrast can be performed with an $EGFR \geq 30$. The assessment for incomplete tumor ablation and local tumor recurrence following thermal ablation procedures are study endpoints that are not based on standardized response criteria, such as RECIST. Instead, the interpretation of follow-up imaging tests is based on identification of findings that are now known to be specific for residual or recurrent tumor. These include new or enlarging nodular enhancing masses either in the ablation zone or at its margins. Enlargement of the ablation zone compared to baseline post-ablation imaging is a suspicious finding. Suspicious findings may undergo biopsy when possible and clinically indicated to prove the presence of tumor. Progressive imaging findings will be a secondary criterion for local tumor recurrence when biopsy is not clinically indicated. Other clinical parameters, such as serum tumor markers, cannot be used as the sole indication that the treated tumor was not treated completely because the marker activity could emanate from other liver tumors or tumor outside the liver. Thus serum tumor markers will not provide direct evidence of local tumor recurrence, but may

CONFIDENTIAL

This document is confidential. Do not disclose or use except as authorized.

provide supportive evidence.

11. ADVERSE EVENT REPORTING REQUIREMENTS

11.1 Definitions

Adverse Event (AE)

An adverse event (AE) is any undesirable sign, symptom or medical condition or experience that develops or worsens in severity after enrollment into the study protocol or any procedure specified in the protocol, even if the event is not considered to be related to the study.

- Abnormal laboratory values or diagnostic test results constitute adverse events only if they induce clinical signs or symptoms or require treatment or further diagnostic tests.

Serious adverse event (SAE)

A serious adverse event (SAE) is any adverse event, occurring during the protocol and regardless of causality that:

- Results in death
- Is life-threatening. Life-threatening means that the person is at immediate risk of death from the reaction as it occurred, i.e., it does not include a reaction which hypothetically might have caused death had it occurred in a more severe form.
- Requires or prolongs inpatient hospitalization (i.e., the event requires at least a 24-hour hospitalization or prolonged a hospitalization beyond the expected length of stay). Hospitalization admissions and/or surgical operations scheduled to occur during the study period, but planned prior to study entry are not considered SAEs if the illness or disease existed before the person was enrolled in the trial, provided that it did not deteriorate in an unexpected manner during the trial (e.g., surgery performed earlier than planned).
- Results in persistent or significant disability/incapacity. Disability is defined as a substantial disruption of a person's ability to conduct normal life functions.
- Is a congenital anomaly or birth defect; or
- Is an important medical event when, based upon appropriate medical judgment, it may jeopardize the participant and require medical or surgical intervention to prevent one of the outcomes listed above. Examples of such medical events include allergic bronchospasm requiring intensive treatment in an emergency room or at home; blood dyscrasias or convulsions that result in inpatient hospitalization, or the development of drug dependency or drug abuse.

Events **not** considered to be serious adverse events are hospitalizations for:

CONFIDENTIAL

This document is confidential. Do not disclose or use except as authorized.

- routine treatment or monitoring of the studied indication, not associated with any deterioration in condition, or for elective procedures
- elective or pre-planned treatment for a pre-existing condition that does not worsen
- emergency outpatient treatment for an event not fulfilling the serious criteria outlined above and not resulting in inpatient admission
- respite care

Expectedness

- Adverse events can be 'Expected' or 'Unexpected.'

Expected adverse event

- Expected adverse events are those that have been previously identified as resulting from administration of the agent. For the purposes of this study, an adverse event is considered expected when it appears in the current adverse event list, the Investigator's Brochure, the package insert or is included in the informed consent document as a potential risk.
- Refer to Section 6.1 for a listing of expected adverse events associated with the study agent(s).

Unexpected adverse event

- For the purposes of this study, an adverse event is considered unexpected when it varies in nature, intensity or frequency from information provided in the current adverse event list, the Investigator's Brochure, the package insert or when it is not included in the informed consent document as a potential risk.

Attribution

Attribution is the relationship between an adverse event or serious adverse event and the study treatment. Attribution will be assigned as follows:

- Definite – The AE is clearly related to the study treatment.
- Probable – The AE is likely related to the study treatment.
- Possible – The AE may be related to the study treatment.
- Unlikely - The AE is doubtfully related to the study treatment.
- Unrelated - The AE is clearly NOT related to the study treatment.

11.2 Procedures for AE and SAE Recording and Reporting

CONFIDENTIAL

This document is confidential. Do not disclose or use except as authorized.

- Participating investigators will assess the occurrence of AEs and SAEs at all participant evaluation time points during the study.
- All AEs and SAEs whether reported by the participant, discovered during questioning, directly observed, or detected by physical examination, laboratory test or other means, will be recorded in the participant's medical record and on the appropriate study-specific case report forms.
- The descriptions and grading scales found in the revised NCI Common Terminology
- Criteria for Adverse Events (CTCAE) version 4.0 will be utilized for AE reporting. All appropriate treatment areas should have access to a copy of the CTCAE version 4.0. A copy of the CTCAE version 4.0 can be downloaded from the CTEP website at:

http://ctep.cancer.gov/protocolDevelopment/electronic_applications/ctc.htm.

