Pyrogenicity (Bacterial Endotoxins)	Q0044, Pyrogen Testing	<175EU/V
Sterility	Q0043, Sterility Testing	No growth after 14 days

Dose administration

The final dose-calibrated, sterile radiopharmaceutical is delivered to the AMIGO suite in a single syringe for intravenous administration through the patient’s existing IV access.

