11.4 Reporting to the Study Sponsor

Serious Adverse Event Reporting

- All serious adverse events that occur immediately after, during, or within 30 days of the research AP-PET scans must be reported to the DF/HCC Overall Principal Investigator on the local institutional SAE form. This includes events meeting the criteria outlined in Section 11.1.2, as well as the following:
 - Grade 2 (moderate) and Grade 3 (severe) Events – Only events that are unexpected and possibly, probably or definitely related/associated with the intervention.
 - All Grade 4 (life-threatening or disabling) Events – Unless expected AND specifically listed in the protocol as not requiring reporting.

CONFIDENTIAL

This document is confidential. Do not disclose or use except as authorized.

- All Grade 5 (fatal) Events – When the participant is enrolled and actively participating in the trial OR when the event occurs within 30 days of the last study intervention.

Note: If the participant is in long term follow up, report the death at the time of continuing review.

- Participating investigators must report each serious adverse event to the DF/HCC Overall Principal Investigator within 24 hours of learning of the occurrence. In the event that the participating investigator does not become aware of the serious adverse event immediately (e.g., participant sought treatment elsewhere), the participating investigator is to report the event within 24 hours after learning of it and document the time of his or her first awareness of the adverse event. Report serious adverse events by telephone, email or facsimile to:

[name]
[contact] (cell)
[contact]
[contact] (office)

- Within the following 24-48 hours, the participating investigator must provide follow-up information on the serious adverse event. Follow-up information should describe whether the event has resolved or continues, if and how the event was treated, and whether the participant will continue or discontinue study participation.

Non-Serious Adverse Event Reporting

Non-serious adverse events will be reported to the DF/HCC Overall Principal Investigator on the toxicity Case Report Forms.

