11.10 Monitoring of Adverse Events and Period of Observation

- All adverse events, both serious and non-serious, and deaths that are encountered from initiation of study intervention, throughout the study, and within 30 days of the last study intervention should be followed to their resolution, or until the participating investigator assesses them as stable, or the participating investigator determines the event to be irreversible, or the participant is lost to follow-up. The presence and resolution of AEs and SAEs (with dates) should be documented on the appropriate case report form and recorded in the participant's medical record to facilitate source data verification.
- For some SAEs, the study sponsor or designee may follow-up by telephone, fax, and/or monitoring visit to obtain additional case details deemed necessary to appropriately evaluate the SAE report (e.g., hospital discharge summary, consultant report, or autopsy report).
- Participants should be instructed to report any serious post-study event(s) that might reasonably be related to participation in this study. Participating investigators should notify the DF/HCC Overall Principal Investigator and their respective IRB of any unanticipated death or adverse event occurring after a participant has discontinued or terminated study participation that may reasonably be related to the study.

CONFIDENTIAL

This document is confidential. Do not disclose or use except as authorized.

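### SAEs are reportable for 30 days, but a patient scanned at 24 hours has no scheduled study evaluation from day 3 to day 89, so most of the window relies on passive ascertainment

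*Combined protocol and SAP*

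**What the plan says.** **The obligation.** Section 11.4 states: "All serious adverse events that occur immediately after, during, or within 30 days of the research AP-PET scans must be reported". Section 11.10 covers serious and non-serious events and deaths "encountered from initiation of study intervention, throughout the study, and within 30 days of the last study intervention should be followed to their resolution". Follow-up may also end when an event is judged stable or irreversible, or when the participant is lost to follow-up. Section 11.4 also sends non-serious events to the principal investigator on the toxicity forms. Section 11.1 defines an SAE without regard to its cause.

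**The ascertainment rule.** Section 11.2 gives one rule for active assessment: "Participating investigators will assess the occurrence of AEs and SAEs at all participant evaluation time points during the study". Its next item requires events to be recorded "whether reported by the participant, discovered during questioning, directly observed, or detected by physical examination, laboratory test or other means".

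**The time points.** The calendar in section 9 has four: screening, day 1, one visit at day 2-30 and one at day 90-365. History and physical examination are marked at screening only. The last two visits list imaging and nothing else. No row is given to adverse events. The same section says "All research activity requiring patient participation occurs during the image-guided liver thermal ablation procedure on day 1" and "Follow-up imaging examinations are performed as part of routine clinical practice and do not require extra patient time or commitment".

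**Usual scan timing.** Section 10 opens the relevant sentence with "While obtaining a contrast-enhanced MRI or CT is routinely performed by our team at 24 hours" and goes on to allow an occasional first scan as late as 30 days for patient-specific reasons. The following scan comes between three months and one year.

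**The concern.** The plan sets a 30-day duty but ties active enquiry to a schedule that, for most patients, stops on day 2 and resumes no earlier than day 90. Nothing in the calendar closes the window with a question to the patient or a look at the record.

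The participant instruction in section 11.10 does not fill the gap. It concerns serious events after the study that could reasonably be linked to taking part. That is narrower than an SAE definition that ignores causality, and it leaves out non-serious events.

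What is at stake is how the safety data can be read. Section 12.2 lists a summary of deaths within 30 days of intervention among the items the DSMC may receive. Without a check at day 30, a nil return cannot be told apart from a patient who was never asked. Completeness would also differ between patients for a reason unrelated to safety, namely the date of the first scan.

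**Working it through.** The plan states no figure for this point, so there is none to reproduce. The check is a day count that sets the reporting window against the calendar.

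Inputs:
- Research scan on day 1 (section 9).
- Window of 30 days (sections 11.4 and 11.10), counted here as days 1-30.
- First post-procedure scan on day *s*, with *s* from 2 to 30 (section 9); usually *s* = 2 (section 10).
- Next scheduled evaluation between day 90 and day 365 (section 9).

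Window days after the last scheduled evaluation inside the window = 30 − *s*.
- *s* = 2: 30 − 2 = 28 days (days 3-30); 28/30 = 93%.
- *s* = 16, as an illustration: 30 − 16 = 14 days; 14/30 = 47%.
- *s* = 30: 30 − 30 = 0 days.

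Sensitivity to the counting rule: if the window runs 30 full days beyond day 1, it ends on day 31. With *s* = 2 the uncovered days are 3-31, which is 29 of 31, or 94%. The choice of rule hardly matters.

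Sensitivity to what happens at the scan visit: the figures above assume that someone asks about adverse events when the scan is done, although the calendar lists only imaging there. If nobody asks, the uncovered days are 2-30 whatever the value of *s*, which is 29 of 30, or 97%.

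Delay until the next scheduled evaluation, for *s* = 2:
- Gap between evaluations: at least 90 − 2 = 88 days, at most 365 − 2 = 363 days.
- Shortest delay for an event in the uncovered period: day 30 to day 90 = 60 days.
- Longest delay: day 3 to day 365 = 362 days.

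These figures count days without a scheduled study evaluation. They do not count missed events.

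**The case against.** The strongest reply is that the passages do not contradict each other. A 30-day reporting duty can coexist with passive ascertainment between visits. Section 11.2 accepts participant reports and discovery by other means. Section 11.4 foresees an investigator learning of an event late, for example after treatment elsewhere. Visit 4 is itself an evaluation time point at which earlier events could come out. All of this stands.

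It rules out several stronger readings that a reader might infer:
- That events from day 3 to day 30 surface only by chance, or that the section 11.10 instruction is the sole safeguard. Other routes exist; they are passive or late.
- That the patient has no contact with clinicians until day 90. The calendar lists protocol events, section 14.1 speaks of clinical follow-up, and the documents are silent on other care in that interval. The supportable statement is that no study evaluation is scheduled.
- That 24-hour SAE reporting presupposes full ascertainment. Under section 11.4 the clock starts when the investigator learns of the event.
- That a definite number of patients is affected. The front sheet gives an enrolment goal of 75, section 14.2 gives a different target, and no proportion scanned late is stated.
- That the 14-day sterility result depends on a patient visit. Section 7 lists it as a radiopharmacy test on ammonia, and nothing links its follow-up to the calendar.

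It can also be said that the stakes are low. The intervention is a diagnostic tracer, section 6 expects no toxicity from the ammonia injection, ablation is standard care, and no objective or planned analysis is a safety endpoint. That lowers the priority without removing the point. SAEs are reportable whatever their cause. Moreover, sections 1.1 and 2.3 allow the research scan to inform margin assessment and further ablation, so events after the procedure are not plainly separate from the research.

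**Conclusion.** The point holds as a mismatch between the safety window and the visit schedule. Followed exactly as written, the plan ascertains 30-day events passively for the usual patient over 28 of 30 days (93%), and active coverage varies from almost none to complete with the date of the first scan.

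This rests on two assumptions. The first is that 24 hours is the usual timing, which section 10 supports without giving a percentage. The second is that adverse events are asked about at the scan visit, which favours the plan.

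Under-counting is the likely direction of any error, but its size cannot be derived from the documents. The primary imaging endpoints and the planned analysis of local progression are untouched. This is a worthwhile, inexpensive improvement to safety capture and does not threaten the trial's main conclusions.

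**What to change.** Add an AE/SAE row to the section 9 calendar at three points: day 1, the first post-procedure scan, and day 30. Make the day-30 item a chart review plus one telephone call, for every patient given a research dose in either arm, whenever the first scan took place. Refer to that row in section 11.2 so that the evaluation time points span the window in sections 11.4 and 11.10.

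The cost is a small workload for existing staff and one case report form page. No visit or test is added.

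The front sheet records permanent closure to accrual in March 2018. For patients already treated, the chart-review part can still be done retrospectively. Where neither part was done, any report should describe the 30-day safety data as passively ascertained.

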11.3 Reporting Requirements

- For multi-site trials where a DF/HCC investigator is serving as the principal investigator, each participating investigator is required to abide by the reporting requirements set by the DF/HCC. The study must be conducted in compliance with FDA regulations, local safety reporting requirements, and reporting requirements of the principal investigator.
- Each investigative site will be responsible to report SAEs that occur at that institution to their respective IRB. It is the responsibility of each participating investigator to report serious adverse events to the study sponsor and/or others as described below.

11.4 Reporting to the Study Sponsor

Serious Adverse Event Reporting

- All serious adverse events that occur immediately after, during, or within 30 days of the research AP-PET scans must be reported to the DF/HCC Overall Principal Investigator on the local institutional SAE form. This includes events meeting the criteria outlined in Section 11.1.2, as well as the following:
 - Grade 2 (moderate) and Grade 3 (severe) Events – Only events that are unexpected and possibly, probably or definitely related/associated with the intervention.
 - All Grade 4 (life-threatening or disabling) Events – Unless expected AND specifically listed in the protocol as not requiring reporting.

CONFIDENTIAL

This document is confidential. Do not disclose or use except as authorized.

- All Grade 5 (fatal) Events – When the participant is enrolled and actively participating in the trial OR when the event occurs within 30 days of the last study intervention.

Note: If the participant is in long term follow up, report the death at the time of continuing review.

- Participating investigators must report each serious adverse event to the DF/HCC Overall Principal Investigator within 24 hours of learning of the occurrence. In the event that the participating investigator does not become aware of the serious adverse event immediately (e.g., participant sought treatment elsewhere), the participating investigator is to report the event within 24 hours after learning of it and document the time of his or her first awareness of the adverse event. Report serious adverse events by telephone, email or facsimile to:

[name]
[contact] (cell)
[contact]
[contact] (office)

- Within the following 24-48 hours, the participating investigator must provide follow-up information on the serious adverse event. Follow-up information should describe whether the event has resolved or continues, if and how the event was treated, and whether the participant will continue or discontinue study participation.

Non-Serious Adverse Event Reporting

Non-serious adverse events will be reported to the DF/HCC Overall Principal Investigator on the toxicity Case Report Forms.

11.5 Reporting to the Institutional Review Board (IRB)

- Investigative sites within DF/HCC will report all serious adverse events directly to the DFCI Office for Human Research Studies (OHRS).
- Other investigative sites should report serious adverse events to their respective IRB according to the local IRB's policies and procedures in reporting adverse events. A copy of the submitted institutional SAE form should be forwarded to: N/A

CONFIDENTIAL

This document is confidential. Do not disclose or use except as authorized.

- The DF/HCC Principal Investigator will submit SAE reports from outside institutions to the DFCI Office for Human Research Studies (OHRS) according to DFCI IRB policies and procedures in reporting adverse events. N/A

